## **Study Protocol**

### **Introduction**

Nearly 18% of United States adults meet criteria for alcohol dependence sometime in their lifetime, with only 24% of those individuals ever receiving any treatment for their disorder (Hasin et al., 2007). The pervasiveness of alcohol dependence indicates a need for continued development of high-impact treatments that are both effective and easily disseminated to a broad population. Recent evidence indicates that Episodic Future Thinking (EFT), the ability to self-project and pre-experience a future event, can help individuals to make changes to habitual behaviors, such as alcohol drinking (Snider et al., 2016). Here, we will evaluate the efficacy of EFT to help individuals reduce alcohol consumption. We anticipate that EFT will result in a reduction in alcohol consumption over a 2-week experimental period when compared to the control group.

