day. They will be allowed to choose any times for the screens, excluding the hours between midnight and 5 am, provided that they are each separated by at least 6 hours. This will ensure that the first and last screens each day will be at least 12 hours apart and the screens will be distributed throughout the day, maximizing the likelihood of detecting alcohol use without placing an unreasonable burden on the participant. Throughout the intervention phase of the experiment, participants will be required to submit three daily breathalyzer assessments at the predetermined times. They will be reminded via text message when a sample is to be collected, and samples will be accepted up to 15 minutes before the scheduled time and 30-60 minutes after the scheduled time, giving the participant 45-75 minutes total to submit the sample. Both groups will receive a \$1 payment for each breathalyzer result submitted within the allowed submission period, regardless of the result of that test. This payment is to encourage participants to complete screens, even if they had consumed alcohol that day. Breathalyzer schedules will be similarly arranged for both groups.

**Intervention.** Participants will be assigned to either the active Episodic Future Thinking (EFT) condition or the control Episodic Recent Thinking (ERT) condition. EFT participants will generate positive future events they are looking forward to and that could happen at different future time points (e.g., in 2 weeks, 1 month, 6 months, 1 year) and participants in the ERT condition will list positive recent events (events that have already happened) that they enjoyed that occurred at different past time points (e.g., 12 hours ago, 24 hours ago, 1 week ago). Participants will be instructed to use and think about their episodic cues as they make decisions. All participants will be provided

with a copy of their episodic cues to take home with them and will receive periodic text messages from research staff to remind them of their cues. Research staff will be available throughout business hours and periodically during evening and weekend hours to deliver text messages and payments. Participants who choose breathalyzer assessment times late at night (e.g., after 8pm) will receive the corresponding payments the following day. Participants will have immediate access to these payments as soon as they are deposited by research staff (see below).

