RMET15-955 Episodic Thinking (ET) as a Candidate Technique to Reduce
Alcohol Consumption

Statistical Analysis Plan

10/26/2017

Statistical Analysis Plan

Descriptive statistics, chi-square, and t-test will be used to compare means and frequencies of sample characteristics among the two groups. Paired t-tests will be carried out to compare alcohol consumption, rates of discounting, alcohol valuation, PANAS measures, and craving scores before and after the intervention within groups. Discounting of delayed money will be assessed using an adjusting-delay task (Koffarnus and Bickel 2014) and an adjusting-amount task (see Du, Green, and Myerson 2002). Discount rate in both tasks will be calculated using the following hyperbolic equation, (Mazur 1987)

$$V = \frac{A}{1 + kD}$$

In this formula, V refers to the discounted value of a delayed reward; A represents the amount of the delayed reward; D equals the delay of the award; and k represents the delay-discounting rate (Mazur 1987). A higher k value means steeper discounting curve and reflects greater impulsivity, while lower k value means shallower discounting curve with less impulsivity. To provide an estimate of k , we will fit the hyperbolic equation to participants' indifference points (given in discounted monetary value), and use its natural log transformation in analyses. All the statistical analyses will be conducted using Prism 7 at a significance level of 0.05.

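### Five outcomes are each tested at an unadjusted 0.05 with no primary outcome and no choice between two discounting tasks, giving roughly an 18-30% chance of a false positive among tests that could support an EFT claim (low to moderate correlation)

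*SAP*

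**What the plan says.** The SAP is a single section. Its outcome analysis is one sentence: "Paired t-tests will be carried out to compare alcohol consumption, rates of discounting, alcohol valuation, PANAS measures, and craving scores", with the comparison made "before and after the intervention within groups". The five outcomes have equal standing. The protocol (Procedures, Intervention) defines two groups: "Participants will be assigned to either the active Episodic Future Thinking (EFT) condition or the control Episodic Recent Thinking (ERT) condition". Each outcome is therefore tested once in EFT and once in ERT.

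Discounting is measured by an adjusting-delay task and an adjusting-amount task. "Discount rate in both tasks will be calculated using the following hyperbolic equation", and the log of k goes into the analyses. The SAP does not say which task supplies the discounting result. PANAS and craving are named in the plural without a number of scores.

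The error rule is: "All the statistical analyses will be conducted using Prism 7 at a significance level of 0.05". The documents give no primary outcome, testing order or adjustment, and do not say whether tests are one- or two-sided.

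The protocol's Introduction states one efficacy expectation: "We anticipate that EFT will result in a reduction in alcohol consumption over a 2-week experimental period when compared to the control group". The SAP does not carry it forward as the lead analysis.

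**The concern.** When one outcome is designated in advance, a 0.05 test of it keeps the risk of a false claim at 5%. When five or more outcomes stand level and each gets its own 0.05, that protection no longer applies to the trial as a whole. If drinking shows nothing but craving, affect or one of the two discounting tasks reaches p < 0.05, the plan contains no rule on how much weight that result may carry. The open choice of discounting task adds a further route to a chance finding. What is at stake is whether a positive report from this trial can be traced to a hypothesis fixed beforehand.

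**Working it through.** **No plan figure to reproduce.** The documents give no power calculation and no family-wise error rate. The only stated figure is the per-test level of 0.05.

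**Inputs**
- Level per test: 0.05 (SAP), taken as two-sided (assumption).
- Outcomes: five named in the SAP, so m = 5 if each yields one score.
- Two discounting tasks (SAP): m = 6 if both are tested.
- Two PANAS scores (assumption; the SAP gives no number): m = 7. Craving is counted as one score throughout.
- Groups: two (protocol, Procedures).
- All null hypotheses true (assumption). Tests comparing sample characteristics are left out.

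**Formulas**
- m independent tests: 1 − 0.95^m.
- m tests with common correlation ρ between the normal test statistics: 1 − ∫ φ(u) [Φ((c − √ρ·u)/√(1−ρ)) − Φ((−c − √ρ·u)/√(1−ρ))]^m du, where c is the two-sided 5% normal critical value. This was integrated numerically.
- Both groups, which are independent of each other: 1 − (1 − one-set rate)².

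**One set of m tests** (EFT group only, or one between-group test per outcome)

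| m | ρ = 0 | ρ = 0.5 | ρ = 0.7 | ρ = 0.9 |
|---|---|---|---|---|
| 5 | 22.6% | 18.3% | 14.8% | 10.2% |
| 6 | 26.5% | 20.7% | 16.4% | 10.8% |
| 7 | 30.2% | 23.0% | 17.8% | 11.4% |

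**Both groups' within-group tests** (2m tests)

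| 2m | ρ = 0 | ρ = 0.5 | ρ = 0.7 | ρ = 0.9 |
|---|---|---|---|---|
| 10 | 40.1% | 33.2% | 27.5% | 19.3% |
| 12 | 46.0% | 37.2% | 30.1% | 20.5% |
| 14 | 51.2% | 40.7% | 32.5% | 21.5% |

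Worked entries: 1 − 0.95^5 = 22.6%; 1 − 0.95^10 = 40.1%; for m = 5 and ρ = 0.5 in both groups, 1 − (1 − 0.1828)² = 33.2%.

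**Drinking alone, tested as the SAP is written.** One paired test in each group gives 1 − 0.95² = 9.75%. Naming drinking as primary without also naming the contrast would therefore not restore 5%.

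**The case against.** **The lead outcome is obvious.** The protocol states one hypothesis, on alcohol consumption; the SAP's title is about reducing alcohol consumption; and that outcome comes first in its list. This stands as an implication. But neither document designates it, and the SAP gives it the same test and level as the other four.

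**The SAP never promises a 5% family-wise rate.** Correct. A reader might infer that the plan misstates its own error rate. It does not: 0.05 is a per-test level, and the gap is that nothing further is specified. Nor does either document say that any significant result may be presented as the trial's positive finding. The plan merely contains nothing to prevent it.

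**33-51% is the wrong headline.** A reader might take the two-group figure as the chance of a false claim for EFT. Half of those tests are changes within the control group, which cannot support such a claim. Nor does the figure carry over to a between-group analysis, where there is one test per outcome and the one-set table applies.

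**The upper figures lean on independence.** This stands in part. Two tasks that estimate the same k are unlikely to be independent, and 30% and 51% also need two PANAS scores. Strong correlation lowers the rates, yet five tests at 0.9 still give 10.2%, twice the nominal level.

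**The all-null model fits pre/post tests poorly.** Participants must want to quit or cut down, and both groups receive cues, daily reporting and breathalyzer screens. Drinking may change in either group with no EFT-specific effect. This stands: under the within-group plan, the percentages are the chance of falsely declaring a change, not of falsely crediting EFT. The absence of an EFT-versus-ERT outcome test is a separate and larger weakness.

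**The other measures may be exploratory.** That would be acceptable, but the SAP does not say so.

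**Conclusion.** The point holds in a limited form. Five named outcomes are tested at an unadjusted 0.05 with no primary outcome and no designated discounting task, although the protocol has one hypothesis. Among tests that could support an EFT claim, the chance of at least one false positive is about 18-30% at correlations of 0 to 0.5 and about 10-18% at 0.7 to 0.9. Counting both groups' tests, it is 33-51% at correlations of 0 to 0.5 and 27.5-32.5% at 0.7.

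These figures assume that all nulls are true, tests are two-sided, and each set holds five to seven tests with a common correlation. The seven-test end needs both discounting tasks and two PANAS scores. The exact rate is uncertain because the documents give neither the number of scores nor their correlations, but no combination examined brings it down to 5%. The documents do not support describing this as a false claim of 5% family-wise control, or quoting 33-51% as the error rate of an efficacy conclusion.

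**What to change.** Change the SAP wording as follows.

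1. Name one confirmatory test: the EFT-versus-ERT comparison of alcohol consumption over the 14-day intervention period, at two-sided 0.05. Define the measure. Mean self-reported drinks per day is one option; the protocol's hypothesis says only alcohol consumption, and average drinks per day appears there as an example for balancing the groups.
2. Name one task's ln(k) as the discounting outcome and treat the other task as a sensitivity analysis.
3. Make discounting, alcohol valuation, PANAS and craving secondary. List each score, with one EFT-versus-ERT test per score. Then either apply Holm over the actual number of tests or label them exploratory. With exactly four tests, the smallest p-value is compared with 0.05/4 = 0.0125; with a second PANAS score there are five, and it is compared with 0.05/5 = 0.01.
4. State that no secondary result can replace the drinking result.

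No new data, visits or participants are needed. The cost is a stricter threshold for the secondary measures under Holm, or less freedom to make claims from them if they are exploratory.
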